5.2.4 Experimental Sessions (Visits 3 and 10 - Overnight Stay)

(Day 1 and approximately 3 weeks later)

CBCT Manual Sessions 4 and 5 practice (Visit 3) and Review (Visit 10)

Sessions 4 and 5 – Satisfaction enhancement and undermining avoidance. Specific content related to listening and approaching, and sharing of thoughts and feelings.

Table 5. Schedule of Procedures for Experimental Sessions

Approximate Time	Procedure or Action		
9:00	Urine drug screen and pregnancy test, participant acclimated to		
	environment, C-SSRS		
9:45	Baseline BP, BT, Pulse, SUD		
10:00	MDMA Administration, Begin video recording		
11:00	SUD		
11:30	BP, BT, SUD, Pulse, Administer optional supplemental dose		
12:30	SUD		
14:00	SUD		
As needed	BP, BT, Pulse		
Every 60-90 minutes	SUD		
Approximately six hours	C-SSRS, General Wellbeing, BP, BT, Pulse		
after drug administration			

Page 46 of 89

The PTSD+ participant and CSO participant will receive two Experimental Sessions of open-label MDMA-assisted psychotherapy in conjunction with CBCT scheduled three weeks apart. Procedures for MDMA-assisted psychotherapy in conjunction with CBCT will remain the same across all sessions, and all procedures will be the same.

Pre-drug:

- a. On the day of the Experimental Session, the PTSD+ participant and CSO participant will arrive approximately 60 to 90 minutes prior to drug administration.
- b. Confirm continuing eligibility by reviewing Inclusion and Exclusion Criteria including medications and adverse events.
- c. Perform a urine drug screen. A positive drug screen will be reviewed by the Clinical Investigator and may be cause for delaying drug administration to a later time, rescheduling the session to a later date, or withdrawing the participant from the study.
- d. If a participant is of childbearing potential, perform a urine pregnancy test. A positive pregnancy screen is cause for withdrawal from the protocol.
- e. If the dyad continues to meet criteria and the dyad reports that they followed appropriate rules and restrictions, the session will proceed.
- f. Review procedures for the Experimental Session with the dyad.
- g. Record the entire session to video and audio. Dyads will be given access to review audio or video recordings of their Experimental Sessions upon request.
- h. The session will last for approximately eight hours or longer, followed by an overnight stay at the study site.
- i. The therapists will administer the C-SSRS to the dyad prior to drug administration.

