5.4 Removal of Participants from the Study

Participants can withdraw consent at any time without prejudice. The therapists can withdraw a participant if, in their clinical judgment, it is in the best interest of the dyad or if the participant cannot comply with elements of the protocol that are critical for safety or for the scientific integrity of the study. If the therapists withdraw a dyad from the study, the therapists will explain the reason for withdrawing the dyad. The reason for early termination will be recorded in both the PTSD+ participant's and the CSO participant's source records and CRF. If one person in the dyad wishes to withdraw, both participants will be dropped from treatment.

Participants will be clinically monitored after withdrawal, the cause of which will be recorded in their source records and CRF. Whenever possible, the tests and evaluations listed for the termination and outcome visits will be carried out. Efforts will be made to obtain information about AE outcomes, if deemed necessary by the PI and/or sponsor.

If a participant develops any Exclusion Criteria that in the opinion of the Medical Monitor, affects the safety of either member of the dyad, including psychiatric diagnosis, pregnancy or excluded medications, the PTSD+ participant will discontinue treatment but remain in the study for follow-up purposes. Whenever possible, the tests and evaluations

listed for the Midpoint, Outcome, and 3-month and 6-month follow-up will be carried out. Efforts will be made to obtain information about AE outcomes, if deemed necessary by the Clinical Investigators, Medical Monitor, and/or sponsor. Dyads who discontinue treatment will not be replaced.

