8.3 Serious Adverse Events

An SAE is defined as any untoward medical occurrence that at any dose:

- Results in death
- Is life-threatening (i.e., the participant was, in the opinion of the Clinical Investigator, at immediate risk of death from the event as it occurred); it does not refer to an event which hypothetically might have caused death if it were more severe
- Requires or prolongs inpatient hospitalization
- Results in persistent or significant disability/incapacity (i.e., the event causes substantial disruption of a person's ability to conduct normal life functions)
- Results in a congenital anomaly/birth defect
- Requires intervention to prevent permanent impairment or damage
- Is an important and significant medical event that may not be immediately lifethreatening or resulting in death or hospitalization, but based upon appropriate medical judgment, may jeopardize the patient/participant or may require intervention to prevent one of the other outcomes listed above

AEs that do not fall into these categories are defined as non-serious. It should be noted that a severe adverse event need not be serious in nature and that a SAE need not, by definition, be severe.

In addition, a pre-existing event or condition that results in hospitalization should be recorded on the medical history. The hospitalization would not result in the event or condition being reported as a study-related SAE unless, in the view of the study physician, hospitalization was prolonged as a result of participation in the clinical trial or

was necessary due to a worsening of the pre-existing condition. This is because the onset of the event (the reason for the procedure) occurred before the participant was entered in the trial. Hospitalization for cosmetics, non-emergency prophylaxis, or abortion does not result in an SAE report unless, in the view of the study physician, hospitalization for these procedures was prolonged as a result of participation in the clinical trial.

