8.5 Adverse Event Collection

The study physician will be responsible for reviewing and confirming all AEs and SAEs collected during the study. The therapists will collect AEs during study/telemedicine visits after enrollment.

All SAEs will be collected for the duration of the protocol. All SAEs which occur during the course of the trial, whether considered to be associated with the study drug or not, have to be reported within 24 hours of the Clinical Investigator's awareness of their occurrence. All SAE reports should be faxed to the sponsor. A fax number will be provided to the site in separate site-specific instruction for SAE reporting. In addition to the fax, the study physician, Clinical Investigator, or designee should call the CRA during normal working hours and verbally inform the CRA of the SAE. During off business hours or if medical advice is needed immediately please call the sponsor Medical Monitor. An SAE reporting instruction with all contact numbers will be provided to the site prior to study start.

Medical Monitor:

Page 69 of 89

[name]. [name] [name] [name] [contact]

Study Monitor contact information will be provided in a separate contact list.

Adverse events that will be collected for the duration of the protocol are:

- All SAEs will be collected through participant termination
- All AEs and spontaneously reported reactions will be collected on the day of drug administration and for seven days after each Experimental Session
- Any spontaneously reported reactions that have not resolved to the PTSD+ participant's or CSO participant's Baseline level of severity after seven days will be collected on the Adverse Event Report page until resolution
- Events requiring medical attention will be collected from enrollment through the PTSD+ participant's or CSO participant's last follow-up
- Events related to planned treatments or physician visits for Baseline conditions collected in the Medical History will not be collected unless there is an exacerbation of the condition
- Any Adverse Event leading to withdrawal from the protocol will be collected throughout the study
- All AEs related to changes in psychiatric status will be collected throughout the study

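### Protocol 5.2.4(d) and 5.4 conflict on follow-up after a positive pregnancy test, 5.4 leaves post-stop follow-up of the CSO unclear, and no procedure follows an exposed pregnancy to its outcome

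*Protocol*

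**What the plan says.** **Pregnancy test before a session.** Protocol 5.2.4(d), which applies to any participant of childbearing potential, states without condition that "A positive pregnancy screen is cause for withdrawal from the protocol".

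**Exclusion criterion arising on study.** Protocol 5.4 opens its rule with "If a participant develops any Exclusion Criteria that in the opinion of the Medical Monitor, affects the safety of either member of the dyad" and continues "including psychiatric diagnosis, pregnancy or excluded medications, the PTSD+ participant will discontinue treatment but remain in the study for follow-up purposes". It then asks, whenever possible, for the Midpoint, Outcome, 3-month and 6-month assessments.

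**Withdrawal.** An earlier paragraph of 5.4 covers withdrawal by the participant or the therapists. It says "If one person in the dyad wishes to withdraw, both participants will be dropped from treatment", and on assessments "Whenever possible, the tests and evaluations listed for the termination and outcome visits will be carried out".

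**Other follow-up text.** Section 5.2.7 (Midpoint) includes dyads, and 5.2.9 (V17 and V18) names both members, where they stopped treatment but continued follow-up. The SAP section on dropouts and missing data asks dropouts for an outcome assessment before long-term follow-up.

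**Safety collection.** The SAE definition in 8.3 includes "Results in a congenital anomaly/birth defect". Section 8.5 says "All SAEs will be collected through participant termination". Section 7.2.5 says the risks of MDMA in pregnancy are unknown. Neither document has a procedure for following an exposed pregnancy to its outcome.

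**The concern.** A site holding a positive test at V10 has two instructions. Under one the person leaves the protocol. Under the other she stops treatment and stays for assessment. The second also depends on a Medical Monitor judgement that the first does not mention.

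Section 5.4 adds two further ambiguities. Its two paragraphs ask for different assessments according to why treatment stopped. Its stay-in-study sentence is triggered by an event in either member but speaks only of the PTSD+ participant. When the CSO has the event, the sentence does not say whether the CSO is followed.

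At stake are comparable post-treatment data across 10 dyads, CSO-reported outcomes (SORTS and the CSO versions of PCL-5, PTGI and TABS), and safety data that 3.4 promises for both members. An exposed pregnancy raises a separate question: whether the study could ever record the outcome that its own SAE definition names.

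**Working it through.** **1. Assessments requested after a stop at V10.** Table 3 schedules CAPS at screening, V16, V17 and V18. The Midpoint (V9) precedes V10, so it has already been collected.

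| Text applied | V16 | V17 | V18 | Members named |
|---|---|---|---|---|
| 5.2.4(d) alone | silent | silent | silent | whoever tests positive |
| 5.4, withdrawal paragraph | sought whenever possible | not named | only if the termination visit means V18 | participants in general |
| 5.4, exclusion-criterion paragraph | sought whenever possible | sought whenever possible | sought whenever possible | PTSD+ only in the stay-in-study sentence |
| 5.2.9, if follow-up continued | n/a | yes | yes | both |

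Table 3 labels no visit as termination; section 9.0 mentions a Study Termination Visit without numbering it. Of the three post-baseline CAPS, the withdrawal paragraph requests V16 and leaves out one (V17) or two (V17 and V18). The exclusion-criterion paragraph leaves out none.

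**2. Scale.** One dyad of 10 is 1/10 = 10%. MDMA goes to 2 × 10 = 20 people, any of whom can trigger the 5.4 rule.

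The plan's own power figure (12.1) reproduces. For a two-sided paired t-test at 0.05 with effect size 0.8 and n = 10, use the noncentral t with df = 9 and noncentrality 0.8 × √10 = 2.53. This gives 61.6%, against 62% stated. If one V16 CAPS were missing and not replaced (n = 9, noncentrality 0.8 × √9 = 2.40), power would be 55.9%. That loss is illustrative; the documents give no dropout rate and do seek V16.

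**3. Timing of a birth relative to SAE collection.** From Table 3: V3 to V10 is about 3 weeks, V10 to V15 about 4 weeks, and V15 to V18 is 6 months, about 26 weeks.

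- V18 falls at 3 + 4 + 26 = 33 weeks after V3, or 34 with the +7-day window in 5.2.9.
- Assumption, not in the documents: birth about 38 weeks after conception. For conception at V3, birth is at week 38. For conception from 2 weeks before to 1 week after V3, it is at 38 − 2 = 36 to 38 + 1 = 39 weeks.
- Weeks 36 to 39 all fall after week 34. Only an early birth would be captured.
- Other sections anchor the 6-month visit differently. Section 12.0 counts from the final Experimental Session, giving 3 + 26 = 29 weeks. Section 4.1 counts from the primary assessment, giving 33 + about 4.3 (30 days) = about 37 weeks, which still precedes 38.
- If a positive test at V10 is treated as leaving the protocol, termination could come as early as week 3.

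Table 3 schedules no pregnancy test after V10, so a pregnancy exposed at V10 would be known only by report. A first positive test at V3 precedes any study drug and is not an exposed pregnancy in this sense.

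**The case against.** The case against a stronger finding is good, and most of it stands.

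- **A reader might infer that a V10 stop loses V16, V17 and V18 by rule.** It does not. Section 5.4 seeks the outcome assessment even after withdrawal, and the SAP asks dropouts for one.
- **A reader might infer that CSO follow-up is not written at all.** Sections 5.2.7 and 5.2.9 include both members, and 5.2.9 lists the CSO measures. Those sections apply only to people who continue follow-up, however, and 5.2.4(d) and 5.4 disagree on who continues. The ambiguity is narrower but remains.
- **A reader might infer that the estimate is confined to dyads who tolerated both sessions.** The SAP's mITT set needs one session and one outcome assessment, and protocol 12.0 keeps available data from those who withdraw. CAPS is measured only in the PTSD+ participant, whom 5.4 expressly retains.
- **A reader might infer that the conflict covers treatment stops generally.** A direct contradiction is shown only for pregnancy. The drug-screen item in 5.2.4(c) is discretionary.
- **A reader might blame the 5.2.4/5.4 conflict for missing pregnancy outcomes.** Step 3 of the working shows that the gap exists even when 5.4 is followed in full.

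Two defences carry less weight. Section 8.1 allows continued follow-up of AEs unresolved at the end, but by case-by-case judgement, and it does not mention pregnancy. The SAP's dropout text is Version 1 of February 2016, predates Amendment 4, and contradicts 5.4 on replacing dyads; the SAP itself defers to the protocol.

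**Conclusion.** The wording conflict between 5.2.4(d) and 5.4 on pregnancy is real and must be reconciled. The two assessment lists and the single-member wording in 5.4 are real ambiguities. Their consequence is inconsistent or incomplete data, chiefly one or two of the three post-baseline CAPS (V17, V18) and CSO outcomes and safety, in a sample where each dyad is 10%. The documents do not support saying that the primary endpoint is lost.

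The missing pregnancy-outcome procedure is a separate gap under either rule. On Table 3, SAE collection stops about 33 weeks after V3 at the latest, so the congenital-anomaly criterion could usually not be observed for a pregnancy exposed at V3 and detected at V10. This rests on the assumed 38 weeks from conception to birth; only under the section 4.1 timing do the intervals come close.

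The correction is worthwhile and inexpensive. It does not call the primary analysis into question.

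**What to change.** 1. Reconcile 5.2.4(d) with 5.4, using terms that separate stopping treatment from leaving the study. This point takes no position on when, or for whom, dosing stops.
2. In 5.4 give one post-stop assessment list, namely whichever of V9, V16, V17 and V18 remain, for both dyad members and whatever the reason, unless a person withdraws consent for data collection.
3. Change the reference to the PTSD+ participant only in the follow-up part of the 5.4 sentence, so that follow-up covers both members. The treatment part is for the sponsor to reconcile.
4. In 8.5 extend collection to the outcome of any pregnancy detected after a dose.

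**Cost.** A protocol wording amendment. V16 to V18 are telemedicine visits already in the schedule. The downside is longer telephone tracking of a rare exposed pregnancy.

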5.2.5 Daily Telephone Contact for Seven Days after an Experimental Session

During daily phone contact:

- a. Starting on the day of the Integrative Session following each Experimental Session, one of the therapists will contact the PTSD+ participant and CSO participant via telephone, telemedicine, or in person every day for one week. The goal of daily contact is assessment of changes in General Wellbeing, safety, and offering support.
- b. The telephone contact will be for a brief check-in lasting five to 15 minutes, or as long as necessary to address any participant's concerns and to assess participants' wellbeing. Additional telephone contact can be initiated at the request of the therapists or participant.
- c. On the second and seventh day of contact after the Experimental Session, the therapists will administer the C-SSRS.
- d. General Wellbeing will be assessed at each phone call.
- e. Spontaneously reported reactions, AEs and Medications will be collected, as described in Sections 8.0 and 9.0.

5.2.6 Integrative Sessions Between Experimental Sessions (Visits 5, 6, 7, 8, 12, 13, 14, and 15 - Telemedicine Visits)

Visits 5, 6, 7, and 8 will occur over 3 weeks between Experimental Sessions 1 and 2 (Visits 3 and 10); Visits 12, 13, 14, 15 will occur over 4 weeks following Visit 10.

CBCT Manual Sessions Review, 6, 7, 8, 9, 12, 13, 14, and 15

Sessions 6 (visit 5) and 7 (visit 6)—Getting UNSTUCK (learning the process of dyadic cognitive restructuring) and problem solving.

Sessions 8 (visit 7) and 9 (visit 8) – Making meaning of the trauma, specifically regarding acceptance and blame.

Sessions 12 (visit 12), 13 (visit 13), 14 (visit 14), and 15 (visit 15) – Making meaning of the trauma. Discussion specifically of themes of emotional closeness, physical closeness, posttraumatic growth, and review and reinforcement of treatment gains.

After each Experimental Session, in addition to the session the following morning, the PTSD+ participant and CSO participant will have four additional Integrative Sessions with the therapists lasting 75-90 minutes each. The therapists may conduct more sessions if they and the PTSD+ participant deem it necessary.

Generally, these sessions include integration of material that emerged as a part of Experimental Sessions and afterward into daily life. Therapists will emphasize their commitment to support the PTSD+ participant during the integration period and will be available via phone or pager. Dyads will be encouraged to relax and rest as much as possible for several days after the Experimental Session.

During Integrative Sessions:

- a. These visits may be conducted by telemedicine or phone.
- b. Record each Integrative Session to audio and video. Dyads will be given access to review one or more Integrative Sessions upon request.
- c. The C-SSRS will be administered just prior to beginning each Integrative Session.
- d. General Wellbeing will be assessed at each Integrative Session.
- e. The PTSD+ participant and therapists will continue to work on supporting the PTSD+ participant as they consider their experiences during Experimental Sessions.
- f. Assess General Wellbeing for both the PTSD+ participant and CSO participant.
- g. Administer the self-report PCL-5 (since last visit) to assess PTSD symptoms for the PTSD+ participant and modified for the CSO participant to rate the PTSD+ participant.
- h. Give the dyad the Out of Session Assignments to be completed after the end of the Integrative Session and returned by the next visit. (Except Visit 15).
- i. The therapists will use clinical judgment to assess the PTSD+ participant's psychological wellbeing. during this period of time. If there are any indications of continuing anxiety or distress, the therapists may arrange to work on reducing the distress at a specially scheduled Integrative Session, through continuing contact, or at the next regularly scheduled Integrative Session. The PTSD+ participant or CSO participant may also initiate contact with the therapists at any time throughout the study.
- i. Collect AEs and medications, as described in Sections 8.0 and 9.0.

5.2.7 Evaluation and Preparation Visit at Midpoint (Visit 9 - Clinic Visit)

(Approximately 3 weeks after V3; prior to V10)

CBCT Manual Sessions 10 and 11

Sessions 10 and 11 – Making meaning of the trauma. Discussion of the themes of trust and control.

The midpoint evaluation will occur approximately 20 days after the first Experimental Session. Dyads who have withdrawn from treatment but have continued for follow-up will also complete this time point. This session will be recorded to audio/video.

- a. The therapists will assess suicidal ideation and behavior with the C-SSRS
- b. General Wellbeing will be assessed
- c. Collect AEs and medications, as described in Sections 8.0 and 9.0

The following self-report measures will be completed at the midpoint:

- PTGI (in reference to time since the trauma) for the PTSD+ participant and modified for the CSO participant to rate the PTSD+ participant
- PCL (since last visit) to assess PTSD symptoms for the PTSD+ participant and modified for the CSO participant to rate the PTSD+ participant
- TABS to assess trauma related beliefs for the PTSD+ participant and modified for the CSO participant to rate the PTSD+ participant
- MDI to assess dissociative symptomology for the PTSD+ participant and CSO participant
- SORTS to assess partner accommodation for the CSO participant
- BDI-II to assess depression symptoms for both the PTSD+ participant and CSO participant
- PSQI to assess sleep quality for both the PTSD+ participant and CSO participant.
 PSQI PTSD addendum will be completed by PTSD+ participant only
- ERQ to assess emotional regulation for both the PTSD+ participant and CSO participant
- TAS-20 to assess emotion recognition, alexithymia for both the PTSD+ participant and CSO participant
- QRI to assess relationship satisfaction for both the PTSD+ participant and CSO participant
- CTS to assess conflict, tactics and aggression for both the PTSD+ participant and CSO participant
- IPF to assess psychosocial functioning for both the PTSD+ participant and CSO participant
- MSIS to assess social intimacy for both the PTSD+ participant and CSO participant
- IRI to assess compassion, empathy and social functioning for both the PTSD+ participant and CSO participant

- IPC for both the PTSD+ participant and CSO participant
- CSI for both the PTSD+ participant and CSO participant, if in a romantic relationship

5.2.8 Primary Assessment (Visit 16 – Telemedicine Visit)

(30 days post Visit 15; window of -2/+7 days)

The PTSD+ participant and CSO participant will repeat all outcome measures with the IR and meet with the therapists again 30 days after Visit 15. This visit may consist of two meetings that may be completed on separate days, one with the IR and the other with the therapists. Session may be recorded to audio/video.

- a. The therapists will assess suicidal ideation and behavior with the C-SSRS
- b. General Wellbeing will be assessed
- c. Last-month CAPS for the PTSD+ participant only will be performed to assess PTSD symptoms, which may be recorded to video in as many instances as necessary to establish inter-rater reliability
- d. Collect AEs and medications, as described in Sections 8.0 and 9.0

The following self-report measures will be completed at the outcome assessment:

- PTGI (in reference to time since the trauma) for the PTSD+ participant and modified for the CSO participant to rate the PTSD+ participant
- PCL (last month) to assess PTSD symptoms for the PTSD+ participant and modified for the CSO participant to rate the PTSD+ participant
- TABS to assess trauma related beliefs for the PTSD+ participant and modified for the CSO participant to rate the PTSD+ participant
- MDI to assess dissociative symptomology for the PTSD+ participant and CSO participant
- SORTS to assess partner accommodation for the PTSD+ participant and CSO participant
- BDI-II to assess depression symptoms for both the PTSD+ participant and CSO participant
- PSQI to assess sleep quality for both the PTSD+ participant and CSO participant PSQI PTSD addendum will be completed by PTSD+ participant only
- ERQ to assess emotional regulation for both the PTSD+ participant and CSO participant
- TAS-20 to assess emotion recognition, alexithymia for both the PTSD+ participant and CSO participant
- QRI to assess relationship satisfaction for both the PTSD+ participant and CSO participant
- CTS to assess conflict, tactics and aggression for both the PTSD+ participant and CSO participant
- IPF to assess psychosocial functioning for both the PTSD+ participant and CSO participant

- MSIS to assess social intimacy for both the PTSD+ participant and CSO participant
- IRI to assess compassion, empathy and social functioning for both the PTSD+ participant and CSO participant
- IPC for both the PTSD+ participant and CSO participant
- RRPQ to assess the process for both the PTSD+ participant and CSO participant
- CSI for both the PTSD+ participant and CSO participant, if in a romantic relationship

